**Study Protocol** 

Table Of Contents
Specific Aims 1
Background and Significance 2
Preliminary Studies 4
Research Design and Methods5
Protection of Human Subjects14
Targeted/Planned Enrollment15
References20

Systemic Lupus Erythematosus (SLE or lupus) is a chronic autoimmune disease that is associated with increased morbidity, mortality, health care costs and decreased quality of life.[1] In the United States, African Americans have three to four times greater prevalence of SLE, risk of developing SLE at an earlier age, and SLE-related disease activity, damage, and mortality compared with Caucasians, with the highest rates experienced by African American women.[2] There is strong evidence that patient-level factors are associated with outcomes,[3] which justifies targeting them with intervention. While evidence-based self-management interventions that incorporate both social support and health education have reduced pain, improved function, and delayed disability among SLE patients,[4] African Americans and women are still disproportionately impacted by SLE.[5] Peer mentoring interventions are effective in other chronic conditions that disproportionately affect minorities, such as diabetes, HIV, and kidney disease, but there is currently no empirically tested peer mentoring intervention developed for SLE patients. Preliminary data from our group suggest that peer mentoring improves self-management, reduces disease activity, and improves health related quality of life (HRQOL) in African American women with SLE.

We propose to test an innovative, manualized peer mentorship program designed to provide modeling and reinforcement by peers (mentors) to other African American women with SLE (mentees) to encourage them to engage in activities that promote disease self-management. Through a randomized, "mentored" or "support group" controlled design, we will assess the efficacy and mechanism(s) of this intervention on self-management, disease activity, and HRQOL. This study is the first of its kind in this field to test peer mentorship as an alternative strategy to improve outcomes in African American women with SLE. This could result in a model for other programs that aim to improve disease self-management, disease activity, and HRQOL in African American women suffering from chronic illness. The immediate goal of proposed work is to determine the efficacy of the program in a randomized design. The long-term goal is to disseminate this potentially cost-effective intervention in diverse clinical and community settings in an effort to improve disease outcomes in African American women with SLE and reduce morbidity and mortality in this high risk group. The following aims will be addressed:

AIM 1: Determine the efficacy of a peer mentorship intervention in African American women with SLE on disease self-management and HRQOL. Hypothesis 1: At 12 months post-randomization, mentees will report improved disease self-management and HRQOL, as measured by the Patient Activation Measure (PAM) and Lupus Quality of Life Questionnaire (LUP-QOL), compared with the social support control group.

AIM 2: Determine the impact of a peer mentorship intervention in African American women with SLE on clinical indicators of disease activity and clinical profile that indicates success of the intervention. Hypothesis 2: At 12 months post-randomization, mentees will show clinical evidence of improved disease activity measured by the patient reported Systemic Lupus Activity Questionnaire (SLAQ) and physician-collected clinical and laboratory SLE disease activity index (SLEDAI) data, compared with the social support control group.

AIM 3: Determine the cost and cost-effectiveness of a peer mentorship intervention on disease self-management, disease activity, and HRQOL, in African American women with SLE. Hypothesis 3: A peer mentorship intervention in African American women with SLE will be cost effective at improving disease self-management, disease activity, and HRQOL, as measured by quality adjusted life years (QALYS), compared with the social support control group.

An exploratory aim will be to determine the role of mediators and moderators of a peer mentorship intervention on outcomes in African American women with SLE, with the hypotheses that disease self-management will act as a mediator and depression, trust, and social support will act as moderators of the relationship between the peer mentorship intervention and disease activity and HRQOL.

The peer mentoring approach is uniquely fitted to African Americans, and this intervention has the potential to lead to health improvements for African American women with SLE that have not been attainable with other interventions. This would significantly reduce disparities and have considerable public health impact.

### **B1. Scientific Premise**

Peer support provides a mechanism for creating a social network on a small scale that augments existing social supports and in which a person receives "support from a person who has experiential knowledge of a specific behavior or stressors and similar characteristics".[1] In studies of predominantly low income and minority populations peer mentors have been shown to help support healthy behaviors including breast feeding, smoking cessation, increased physical activity, and maintenance of weight loss,[2-9] along with improved medication adherence and blood glucose monitoring in trials of people with diabetes.[10-16] Similarly, support group participation for women and patients with cancer and other chronic conditions has a positive impact in various areas, including quality of life, cognitive function, and fatigue.[17-32] These studies highlight the potential of peer support, and peer mentoring specifically, as a culturally sensitive means to improving health behaviors and outcomes in low income and minority groups in whom trust in the health care system may be lower than in the general population.[33-36] Previous results have shown that African American patients with SLE were more likely than white patients to have higher levels of unmet needs related to health care and information,[35,37,38] which may preclude adequate disease management[39] and contribute to persistent disparities. There is some evidence that peer mentoring has led to improvements in positive affect, sleep. social coping, and perception of bodily pain in rheumatic conditions, but there is no such peer mentoring intervention developed for SLE patients.[40,41] As a result, this study will bridge this gap in knowledge by testing a peer mentoring intervention for African American women with SLE wherein modeling and reinforcement of disease self-management skills by peers (mentors) to other African American women with SLE (mentees) will be achieved through a combination of educational and informal phone or video interactions with each other, along with the use of validated measures of patient reported outcomes and clinical indicators of disease activity to assess the efficacy of the program.

### **B2. Significance**

This proposal addresses the mission of the National Institutes of Health (NIH) to promote and improve the health of individuals, families, and communities by proposing: 1) clinical research on health and illness that integrates the behavioral and biological sciences; 2) science to help people strengthen the quality of their lives; and 3) development of a personalized approach to maximize health and well-being for individuals. Specifically, this study will test a culturally tailored intervention that promotes better understanding and management of a chronic condition by engaging individuals as active participants in their own health, in an effort to prevent illness and promote health. This project is designed with the long term goal of improving disease selfmanagement and quality of life, and decreasing indicators of disease activity among African American SLE patients and African American women suffering from other chronic illnesses. Addressing the public health burden of SLE. SLE (or lupus) is a chronic autoimmune disease affecting over 250,000 individuals that is marked by acute periodic flare-ups of symptoms impacting any organ system and resulting in potentially life-threatening complications.[42-44] Additional annual costs associated with SLE are estimated to be \$10,000-\$50,000.[45-51] Healthrelated quality of life (HRQOL) of patients with SLE is also significantly worse and affects all health domains at an earlier age compared to patients with other common chronic diseases and females in the general US population.[52-58]

Acknowledging challenges in SLE disease self-management. Evidence-based self-management interventions designed to enhance social support and provide health education, among lupus

patients, have reduced pain, improved function, and delayed disability.[59,60] Specifically, arthritis self-management education delivered by small-group, home study, computer, and Internet modalities have demonstrated significant improvements in health distress, self-reported global health, and activity limitation,[17,61-65] but African Americans and women are still disproportionately impacted by SLE.[66-71] Persistent disparities may be due to the non-responsiveness of existing programs to the unique needs of African Americans and/or women with SLE.[35,37,59,60,72] Studies that have explored adverse outcomes in SLE patients have acknowledged the role of understanding the medical regimen, trust in the provider, and communication with providers, which are impacted by patient subjective norms, cultural, social support networks, mental health, and education. Many patients lack the education, social support, self-efficacy, and trust necessary for effective disease self-management, and these trends are more pronounced in African-Americans than Caucasians.[73-76]

Attending to unique needs within the African American community. Previous results have shown that African American patients with SLE were more likely than white patients to have higher levels of unmet needs related to health services and information.[35,37,77] These domains have included issues such as: 1) understanding the medical regimen, including considerations around depression, medication concerns (possible side effects and interactions), and physical symptoms (pain and fatigue), 2) trust in the provider, 3) communication with providers, 4) receiving adequate information from medical staff about treatment side effects, 5) having access to telephone support and advisory services, and 6) having assistance with knowing which symptoms should trigger a doctor visit.[35,37] Such deficits are compounded by findings that doctors may not be skilled in determining their needs and the barriers that lupus patients experience,[38] which may preclude adequate disease management[39] and contribute to persistent disparities.

Targeting racial disparities in SLE. In the United States, the highest lupus morbidity and mortality rates are among African American women. [43,47,60] SLE affects approximately 1 in 250 African American women of childbearing age, and African Americans overall have three to four times greater prevalence of lupus, risk of developing lupus at an earlier age, and lupus-related disease activity, damage, and mortality compared with Caucasians. [66,70,78-80] Some have positioned elevated rates of SLE in African American women in the context of "immune cognition", and suggest that the disease, for these women, is a physical manifestation of patterns of stress, discrimination, and social disadvantage. [68,71,81-85]

Proposing peer mentoring as a solution to enhance self-management and improve outcomes. Peer mentors are usually individuals who have successfully coped with a similar condition as their mentees.[1] In formal interventions, mentors receive training focused on communication skills, including empathetic listening, helping mentees clarify life goals, and problem solving with the aim of having the mentor support the mentee.[86] In previous studies of predominantly low income and minority populations, and those focused on rheumatologic conditions, peer mentors have been shown to help support healthy behaviors[2-16] and improvements in quality of life.[40,41] In the Peer Approaches to Lupus Self-management (PALS) intervention pilot study, mentees showed a trend toward lower disease activity, higher quality of life, lower pain symptoms and higher social support (effect sizes >0.3) following participation in the intervention. In addition, both mentees and mentors gave very high scores for perceived treatment credibility and service delivery.[87,88]

Recognizing the importance of cultural tailoring to the success of behavioral intervention. Since African American women are a highly marginalized population, it is imperative to explore disease self-management approaches that are culturally acceptable, effective, and inexpensive in order to have the potential to impact chronic disease outcomes on a large scale.[36] The proposed PALS intervention incorporates culturally-relevant components that are likely to mitigate the high burden of SLE and poor outcomes of the disease in African American women. Current data show that culture-specific or culturally enhanced programs for minorities are more effective in improving health outcomes than generic programs or other control conditions.[89-91] The proposed PALS intervention has adhered to the five accepted stages of cultural adaptation:[92] information gathering was achieved through extensive literature review and ascertainment of patient and participant feedback,[59,60,93-95] preliminary design built upon lessons learned from prior behavioral interventions in the same patient population,[93,96] preliminary testing was achieved by piloting the proposed intervention in a limited sample,[87] refinement involved

incorporating participant responses and lessons learned into the final design of the proposed intervention, [97,98] and the final trial is currently being proposed.

#### **B3.** Innovation

The project is innovative because it will be the first study to test peer mentorship as an alternative strategy to improve outcomes in a high risk population with SLE. Innovative aspects of the proposed study include: 1) Developing and testing a culturally relevant intervention in an understudied disease (lupus) and underrepresented population (minority women); 2) Recruiting from a community sample of peers, making it more grassroots and easier to deploy elsewhere; 3) Accounting for financial feasibility and long-term dissemination by using peers as mentors; and 4) Using a structured approach for matching mentors to mentees to ensure effective communication and adherence to study protocol. Given the success of the peer mentoring approach in other chronic conditions that disproportionately impact minorities, and its responsiveness to the needs of this unique population, this intervention is likely to result in health improvements that have not been attainable with other interventions and serve as a sustainable solution to persistent disparities in this population. Specifically, this study is innovative is that it is culturally tailored to the unique needs of African American women with SLE, will pair mentees with mentors who are race, gender, and SES concordant to facilitate bonding and social support, and will use peer mentors who are considered competent in the management of their condition in order to provide modeling and reinforcement to participants. To ensure that the PALS project is a true translational effort that addresses the context of African American women's lives (e.g., social determinants of health), we analyzed qualitative responses of mentees that were collected as part of weekly checkins over the course of the 12-week pilot and an end-of study semi-structured focus group to generate feedback. Qualitative inquiries and responses served as our participatory process in further refining and culturally adapting the intervention protocol.[97]

### Feasibility & Preliminary Data Relevant to the Proposed Work

1. Investigative Team. This multidisciplinary team is well qualified to carry out the proposed study. [name] is a new minority investigator who has recently completed her K01 award (Grant number 1K01AR060026). Her team of senior investigators complement her expertise and will provide complementary expertise. The team has worked together on both her K01 and the pilot study for this grant and this application represents a logical extension of the group's program of research geared toward improving outcomes for African American women with SLE. 2. The Balancing Lupus Experiences with Stress Strategies (BLESS) intervention (Clinical Trials.gov Identifier: NCT01351662)Our team validated a stress management program and assessed its effectiveness in reducing perceived and biological indicators of stress in 30 African American lupus patients participating in the SLE Clinic Database Project at MUSC. The intervention included 6 weekly, group sessions (n=15) of the "Better Choices, Better Health" Chronic Disease Self-Management Program (CDSMP). The patients randomly assigned to the control condition (n=15) received general disease information and relevant literature. Pre, post, and follow up (3-4 months post-intervention) measures were collected in all patients to assess the effectiveness of the program. Overall, we found that patients who received the intervention reported improved self-efficacy pertaining to coping with having lupus, less health distress, post intervention, and lower levels of depression, compared with controls, and concluded that the intervention workshops acted to reduce perceived stress and improve quality of life.[93,105,106] 3. Intervention to Improve Quality of life for African-AmericaN lupus patients (IQAN) (ClinicalTrials.gov Identifier: NCT01837875) We conducted an RCT that assigned 50 subjects each to one of three treatments groups: 1) a unique 'a-la-carte' self-management program with individualized intervention plan (IIP) including a mail-delivered arthritis kit, addition and access to a message board, participation in a support group, and enrollment in a local self-management program; 2) a 'set menu' that offered a standardized chronic disease self-management program only; and 3) a control group that received usual care (UC),[96] At 6 months of follow up, the 'a-lacarte' group had significant improvements in lupus disease activity, QOL, and stress/pain management compared to the control group. Based on feedback from subjects in the BLESS

study, the most valued aspect of the program was interaction with their peers, which informs the proposed intervention.

4. The Peer Approaches to Lupus Self-Management (PALS) Pilot Study. The PALS intervention was piloted with African American women with lupus enrolled in the SLE database at MUSC. Seven mentors were trained and paired with 21 mentees to provide modeling and reinforcement to participants by telephone for at least 60 minutes every week for 12 weeks. Mentee outcomes of self-management, disease progression (including disease activity, damage, and cytokine balance) were obtained at baseline, mid-intervention (6 weeks from baseline), and immediately postintervention (12 weeks from baseline), using validated tools. Qualitative data were also collected over the course of the study in the form of weekly mentee check-ins, mentor logs, and an end-of study focus group. While the PALS pilot lacked a control group, it provided a sense of general effect size and was used to design the current study.[107,108] At post-intervention, we observed statistically significant decreases in patient-reported disease activity (significant change score of 24,70 or 25% change in patient global assessment of overall lupus disease activity, p<0.001). incrementally improving trends in patient activation, and statistically significant decreases in depression (significant change score of 2.62 or 11% change in PHQ-8 score, p=0.05) and anxiety (significant change score of 3.52 or 15% change in GAD-8 score, p=0.018). Student t tests were also conducted to compare 2-month pre- and 2-month post-intervention hospitalization charges. Mean charges per person were \$24289 prior to intervention and \$872 post intervention, providing very strong evidence for the intervention's potential to reduce inpatient charges post intervention.[109] In addition, both mentees and mentors gave very high scores for perceived treatment credibility and service delivery, providing preliminary support for the efficacy, acceptability, and perceived credibility of the PALS intervention.[87,88,97] In summary, our preliminary studies demonstrate that in African American women with SLE, selfmanagement education delivered in weekly sessions led to improvements in lupus self-efficacy, health distress, and depression, and that more culturally targeted information and increased social support could yield more significant improvements in quality of life. More importantly, results of BLESS and IQAN studies, feedback from patients, extensive review of the literature and preliminary data from the PALS pilot study suggest that a peer mentoring intervention is credible, acceptable and likely to be effective at improving self-management, decreasing disease activity and improving quality of life in African American women with SLE. Additionally, using the same outcome measures across investigations will allow comparison of the impact of the current culturally tailored approach to the untailored "Better Choices, Better Health" intervention used in the BLESS study with this patient population.

# B4. Approach

B4a. Theoretical Basis for Peer Mentoring

The Main Effect Model of Social Support posits that it is social relationships, and the support received from them, that are the primary drivers of improvements in both physical and mental health.99 The proposed peer mentoring intervention for African American women with SLE fits within a social support model that we hypothesize will influence this main effect by inducing downstream effects on health-related quality of life, mental well-being, and immune function, as it relates to disease activity. Within this model, we expect peer mentoring to reduce feelings of isolation and loneliness; provide culturally tailored, experiential, and evidence based education and information about accessing available health services; and promote behaviors that positively improve disease self-management, health-related quality of life, and disease activity.[86,100,101]

B4b. Study Overview. The Peer Approaches to Lupus Self-Management (PALS) study is a randomized controlled trial designed to examine whether a new, culturally tailored peer mentoring intervention improves disease self-management, indicators of disease activity, and health related quality of life (HRQOL) in African American women with systemic lupus erythematosus (SLE). African American women with active SLE will be recruited as mentees and peer mentors. We will recruit 300 mentees (150 mentored and 150 support group) and up to 60 mentors. As part of each wave, mentors (n=20) will be trained to deliver intervention content, prior to being paired with up to three mentees (n=50). The peer mentoring intervention will occur by twelve 60-minute telephone or video sessions carried out across the course of 24 weeks. In each wave, social support controls (n=50) will participate in a lupus support group

created for this project, on the same schedule as peer mentoring sessions. Both conditions will be delivered via Webex, which has several advantages for this intervention: 1) Sessions are easily accessible via phone or computer, allowing participants to choose their preferred interaction style; 2) A study coordinator can host the support groups and drop in/out for monitoring purposes; 3) There are video- or voice-call options for up to 25 participants at a time; and 4) This application ensures concordant delivery methods across both arms of the study and the ability to document the frequency that voice and video options are used to adjust for participant choices in analyses. All participants (mentees, mentors, and social support controls) will be assessed using validated measures of patient reported outcomes and clinical indicators of disease activity at baseline, mid-intervention (3 months from baseline), immediately post-intervention (6 months from baseline), and 6 months post-intervention (12 months from baseline). For each wave, outcomes for mentees randomized to the mentored group will be compared with the outcomes of mentees randomized to the support group. A booster session will be incorporated for all participants (mentored and support group) at 3 months post-intervention to encourage retention.[102]

B4c. Scientific Rigor: Assuming 3 post-randomization measurement time points, level of significance p=0.05, two-tailed comparison, correlation between pairs of measurements within participants (interclass correlation) no larger than p=0.7, AR(1) covariance structure, we estimate that 123 participants per group (total n=246) are needed to detect, with 80% power, a standardized effect size of 0.35sd with 20% inflation for attrition at 12 months. This study will apply strict principles of randomized clinical trials including randomization, blinding, careful tracking of all participants and intent-to-treat analyses to ensure robust and unbiased results.

B4d. Consideration of Relevant Biological Variables: This study considers race/ethnicity, gender, age and comorbidity as relevant biological variables. Race/ethnicity, gender, age and comorbidity will be based on self-report. The primary population of interest is self-reported black or African American women. While the burden of SLE (e.g., prevalence, severity, prognosis) is higher across a number of ethnic/racial groups in addition to African Americans, compared to Whites,[43,103,104] we have chosen to establish the efficacy of the intervention in the highest risk group (African American women). Exploratory analyses will be performed, stratified by age (<25 years, 25-34 years, 35-44 years, 45-54 years, 55-64 years, and >65 years) and number of comorbidities (0/1 vs. >2) to evaluate the differential effect of the intervention by age and number of comorbidities.

Methods for AIM 1: Determine the efficacy of a peer mentorship intervention in African American women with SLE on disease self-management and HRQOL

B4f. Study Population & Recruitment Plan

Study Population/Feasibility of Recruitment. The study population are individuals with SLE at MUSC clinics. Preliminary review of electronic medical records show that there are 1000 African American female patients with SLE who have been seen in MUSC clincis in the last year. Of these, 501 patients are enrolled in a longitudinal SLE registry at MUSC. A total of 520 African American female SLE patients (283 MUSC-wide and 237 registry) have consented to be approached for research studies. While 113 of these potential participants have participated in our prior research (thus excluding them from the current study as mentees), approximately 30 new eligible patients are expected to be seen in MUSC lupus clinics each year, bringing our recruitment pool to N=557 for mentees. Prior participants will be eligible to participate as mentors. All patients have American College of Rheumatology (ACR) criteria and disease activity information available, as well as quality of life measures available in the database. All SLE patients meet at least four components of the 1997 ACR revised criteria for SLE.[110] Our team has a successful track record of recruiting minorities into clinical trials. For example, [name] has completed 5 clinical trials with minimum of 12 months of follow up that enrolled only African Americans, the PI was able to successfully enroll 30 African American women with SLE for her BLESS study and 150 African American participants for her IQAN study within proposed recruitment periods, and for the PALS pilot. attrition was only 10%. We will use previously effective strategies for recruitment and retention including adequate patient incentives, use of minority study coordinators, token gifts at baseline visits, mailings to all participants in recognition of their personal life events, such as birthdays, births, graduations, and wedding anniversaries, certificate of completion, and a celebration at the end of each intervention wave that brings all participants together [111,112] We are confident that these strategies will maximize recruitment and retention for the study.

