Power and Sample Size Justification: The sample size calculation and power analyses are based on the primary outcome of change in HRQOL between baseline and 12 months post intervention. The minimum sample size was based on detecting a clinically meaningful difference of 0.35 standard deviation units (medium effect) based on prior studies.[87,93,139-143] Essentially, this is equivalent to testing the interaction between time and group. Assuming 3 measurement time points, level of significance p=0.05, two-tailed comparison, correlation between pairs of measurements within participants (interclass correlation) no larger than p=0.6, compound symmetry covariance structure, we estimate that 123 participants per group (total n=246) are needed to detect, with 80% power, a standardized effect size of at least 0.35sd. This sample size includes a 20% inflation for attrition at 12 months. This effect size is robust enough to provide sufficient power for the outcomes listed under aims 1 and 2 and is consistent with data from our pilot study of 20 mentees and 7 mentors (see preliminary data). The pre-post differences in the outcomes (such as overall social support, positive social interaction, tangible support, vitality, emotional support, social functioning, general health, coping, etc), ranged from 0.35 to 0.88 standard deviation units. Although these calculations account for within patient clustering through the intera-class correlation mentioned above, clustering within mentors and mentees are assumed to have minimal intra-class correlation based on pilot data, especially since the cluster sizes would be at most 3 at a given wave. However, a multi-level model will be used in the analysis to verify this. Since the effect size planned is conservative, if the clustering leads to higher intra-class correlation, we would still be able to detect meaningful differences. We will also consider including mentor as a fixed effect in the model.

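### The plan asks whether the intervention effect differs by age and comorbidity, but specifies only stratified exploratory analyses and no treatment-by-subgroup interaction

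*Combined protocol and SAP*

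**What the plan says.** Section B4d (Consideration of Relevant Biological Variables) names age and comorbidity as relevant variables. It says "Exploratory analyses will be performed, stratified by age", lists the six bands ("stratified by age (<25 years, 25-34 years, 35-44 years, 45-54 years, 55-64 years, and >65 years"), and adds "number of comorbidities (0/1 vs. >2) to evaluate the differential effect of the intervention by age and number of comorbidities". It names no model, contrast, test or rule for comparing strata.

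The rest of the document does not supply one:

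- Power and Sample Size Justification frames the primary test as time by group.
- The Aim 1 analysis in the Overview of Statistical Analysis Plan has treatment, time and their interaction. Demographic factors enter only as covariates.
- The Aim 2 analysis has time by group, plus possible interactions among SLEDAI components in the responder model.
- The exploratory mediator and moderator analysis lists psychosocial and care-related variables, with neither age nor comorbidity among them. Its Wald test compares post-baseline with baseline measurements, not arms across subgroups.

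The design figures are "We will recruit 300 mentees (150 mentored and 150 support group) and up to 60 mentors" and, for power, "123 participants per group (total n=246) are needed to detect, with 80% power, a standardized effect size of at least 0.35sd". No stratum sizes or stratum power are given.

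**The concern.** Whether an effect differs between groups is a question about the difference between stratum effects. A set of within-stratum estimates or p-values does not test that difference. A band can reach significance while its neighbour does not because of size and chance alone, and the smaller the bands the more often this happens.

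What is at stake is a statement about who benefits. B4d presents these variables as biologically relevant, so the stratum results could be used to describe for whom mentoring works. The primary and secondary comparisons, the sample size and the safety rule do not depend on this analysis.

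**Working it through.** **Inputs from the documents.** 300 mentees, 150 per arm (B4b); two-sided 0.05, 80% power, 0.35 SD, 20% attrition, correlation 0.6 with compound symmetry (Power and Sample Size Justification); correlation 0.7 with AR(1) (B4c); six age bands and two comorbidity groups (B4d).

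**Assumption.** Equal strata, because the documents give no age or comorbidity distribution.

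**The plan's own figure first.** For a single measurement, n per group = 2(1.96+0.84)²/0.35² = 128.1.

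- Change from baseline, compound symmetry 0.6: variance factor 2(1-0.6) = 0.80; 128.1 × 0.80 = 102.5; × 1.2 = 123.0. This matches 123.
- Mean of three post-baseline measurements, AR(1) 0.7: factor (3+2(2×0.7+0.49))/9 = 0.753; 128.1 × 0.753 = 96.5, rounded up to 97; 97/0.8 gives 122. This is within one of 123.
- Mean of three post-baseline measurements, compound symmetry 0.6: factor (1+2×0.6)/3 = 0.733. This does not reproduce 123 (it gives 118), but it serves as a lower bound on the variance.

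The variance factor is therefore carried as 0.73 to 0.80.

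**Stratum sizes.** 300 × 0.8 = 240 evaluable. Per arm: 240/12 = 20 in each age band and 240/4 = 60 in each comorbidity group.

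**Power within a stratum at 0.35 SD.** SE = sqrt(2f/n), power = Φ(0.35/SE - 1.96).

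- Age band, f = 0.80: SE = sqrt(1.6/20) = 0.283; Φ(1.237-1.96) = 0.235. At f = 0.733 it is 0.252. So about 24-25%.
- Comorbidity group, f = 0.80: SE = sqrt(1.6/60) = 0.163; Φ(2.143-1.96) = 0.573. At f = 0.733 it is 0.610. So 57-61%.
- The difference detectable with 80% power in one age band is 2.80 × 0.283 = 0.79 SD at f = 0.80, more than twice the planned effect.

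**Same true effect everywhere, strata read by significance.** The chance that at least one age band is significant and at least one is not is 1 - p⁶ - (1-p)⁶.

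- p = 0.235: 1 - 0.0002 - 0.200 = 0.80.
- p = 0.252: 1 - 0.0003 - 0.175 = 0.82 to 0.83.
- For two comorbidity groups, 2p(1-p) = 0.48 to 0.49.

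**No effect anywhere.** The chance of at least one p<0.05 is 1 - 0.95⁶ = 0.265 over six age bands and 1 - 0.95² = 0.0975 over two comorbidity groups.

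**Sensitivity to attrition.** If all 300 women were retained (25 per arm per band), within-band power would be 28-30% and the chance of a mixed pattern under one common effect 86-88%. The conclusion does not turn on the attrition figure.

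**What an interaction test would offer.** For the two comorbidity groups, the SE of the difference in effects is 0.163 × sqrt(2) = 0.231 at f = 0.80.

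- Power for a 0.35 SD difference is Φ(0.35/0.231 - 1.96) = 0.33, rising to 0.35 at f = 0.733.
- The difference detectable with 80% power is 0.62 to 0.65 SD.
- A 5-df test over the age bands has about 15-16% power for an illustrative pattern of 0.70 SD in one band and 0.28 SD in the other five.

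**The case against.** The strongest reply is that B4d does not say the strata will be compared by significance. It gives no comparison rule, the analysis is labelled exploratory, and the Aim 1 and exploratory sections stress effect estimates with 95% CIs. Laying stratum estimates side by side is a legitimate descriptive look at heterogeneity. This stands in part: the 80% and 26% figures are conditional on a reading by significance that the plan does not state. It does not remove the gap, because the stated purpose is to evaluate a differential effect and no section estimates or tests that quantity.

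A second reply is that the interaction tests are themselves underpowered. That is true and limits what the fix can deliver, but a wide interval around the right quantity is more useful than a mixed set of p-values on other quantities.

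Two stronger readings are tempting and are not supported:

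- A reader might infer from the printed cut points ("55-64 years, and >65 years", and 0/1 against >2) that women aged 65 and women with exactly two comorbidities are left out. The groups are otherwise contiguous, and an underlined > loses its bar when text is read from PDF. That ≥ survives in the Aim 2 analysis shows only that some such symbols came through. The documents give no comorbidity distribution from which to count excluded women.
- A reader might pool all eight strata and quote 1 - 0.95⁸ = 34% as the chance of a false positive. The age and comorbidity strata contain the same women and are not independent, so that figure is not relied on.

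**Conclusion.** The concern holds as an omission: the plan sets out to evaluate differential effect by age and comorbidity and specifies no analysis that tests it. Under equal bands, 300 recruited, 20% attrition and a variance factor of 0.73 to 0.80, each age band has about 20 evaluable women per arm and 24-25% power at 0.35 SD. If the bands were read by significance, a uniform effect would look uneven about 80% of the time, and a null effect would give at least one significant age band 26% of the time. Unequal bands would lower power further in the smallest ones.

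The documents do not show that anyone is excluded by the cut points, nor that the investigators will declare subgroup effects from p-values. The point is minor, because the analysis is exploratory and touches no primary or secondary comparison, but it is easily put right.

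**What to change.** In B4d and in the statistical analysis section, state that differential effect will be assessed by adding arm-by-time-by-age (age continuous) and arm-by-time-by-comorbidity terms, with their lower-order terms, to the planned mixed model. Report the interaction estimates, in particular the 12-month contrasts, with 95% CIs and label them exploratory. Keep the band-by-band estimates as description only.

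The cost is SAP wording and a few model terms, with no new data or participants, since B4d already plans to collect age and comorbidity by self-report. There are two downsides. Power stays low, at about 33-35% for a 0.35 SD difference between comorbidity groups. A linear age term can miss a non-linear pattern, which the descriptive bands would still show.

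Separately, check in the source document that the top groups read ≥65 and ≥2. This is a check of the symbols, not a claimed error in the plan.
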